Patient characteristics to be recorded: Age (in years), gender (Male/Female), presence of diabetes diagnosis (any "no" would be excluded from study), smoking behavior (Yes/No), presence or absence of pedal pulses (Yes/No) and Ankle Brachial Index (ABI), relevant laboratory values, culture reports and other pertinent medical history (co-morbid conditions). Additionally, telephone numbers will be obtained, with the participants consent, in order to call and remind the participant the day before there next upcoming visit.

Inclusion criteria: (1) Veterans over 21 years of age; (2) with chronic lower extremity or diabetic foot ulcers (wound duration over 8 weeks); (3) who at the clinician's judgment requires wound debridement (25% or more of wound bed covered with non-viable tissue); (4) wound size 1.5 cm (roughly the size of a quarter) or larger in diameter.

Exclusion criteria: (1) Cognitive impairment that would interfere with patient signing own Informed Consent; (2) Veterans on active anticoagulant therapy with most recent (within last week) PT/INR (international normalized ratio of prothrombin time) > 3.0, or other significant bleeding risk; (3) Active immune suppression just prior to or during study (on systemic corticosteroids* within 7 days prior, or chemotherapy for cancer or RA treatment within 4 weeks prior to study, or with diagnosis of HIV/AIDS) - *Nasal steroid sprays will not be excluded; (4) Active systemic antibiotics is an exclusion; (5) Absent dorsalis pedis pulses and Ankle Brachial Index (ABI) < 0.5 is an exclusion (indicates critical limb ischemia). Other possible reasons participants could be removed from this study include: transfers to other non-VA facilities, participant is unable to tolerate tissue sampling even with local anesthesia, at the discretion of the provider for clinical reasons, and/or inability to comply with scheduled research visits. Furthermore, if the participant has significant wound healing so that sampling is not possible after the initial sampling, they will be removed from the study.

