Larval Debridement Therapy (intervention) group: Briefly, wounds may be rinsed with saline and blotted with sterile gauze prior to collecting baseline wound samples at Day 0. Wound measurements and wound photos will be taken at baseline and Day 8. Wound samples will be collected on Day 0, Day 4, and Day 8. One BioBag (larval debridement therapy) will be applied to wound on Day 0 after baseline wound samples are obtained, and this will be removed on Day 4, at which time 2nd wound sample is obtained. Immediately after 2nd wound sample obtained, the 2nd BioBag will be applied. The dead larvae from the Biobags after removal from the subjects in this study will be placed in a sterile container and labeled with study subject number and "1st" or "2nd application." These specimens will be frozen in our VA research laboratory for a future secondary analysis. This will be the subject of a new grant proposal being submitted by the current investigators in 2015 with the aim of examining the digestive track and body of the larvae for the presence of bacteria and correlating this with the bacteria identified in the bacterial analysis of the subject wounds. Size of the Biobag is determined by the size of the wound (typically 5 to 8 larvae per cm² or 50 to 400 larvae per single Biobag). Only cover dressing (saline moistened gauze + dry gauze/secondary cover) will be changed over BioBag on days 1,2,3,5,6, and 7. Last wound sampling (3rd) will be done on Day 8, after 2nd BioBag is removed. Clinicians as well as Veteran participants and non-Veteran participants (at NFRMC) and their caregivers will be given copies of LDT instructions for use (Appendix A/Appendix B). Wound samples will be obtained at each

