sampling date by sterile swab(s) and 3-4mm curette scraping of wound bed using a sterile curette sweeping z track method across wound bed. Sterile filter paper or micropipette/capillary tube may also be used to collect wound fluid. Wound samples will be collected at wound provider's office/clinic and placed in appropriate receptacle (sterile transport tubes with caps or vials with caps) for transport. The sample receptacles will be labeled with assigned subject number, number of visit (1, 2, 3, etc.), date of sample collection, duration and location of wound. Labeled samples will be placed in sealed biohazard bag, then in a biohazard marked cooler with a cold pack, and this container will be placed in a larger transport container for transport to the VA laboratory. Clinicians and clinic staff will be asked to complete sample collection training and biohazard shipping (if shipping is deemed necessary) training before collecting or shipping any wound samples to standardize the procedures and be in compliance with research, safety and shipping regulations. Clinicians will be asked to view a LDT training video before performing application of Larvae in order to further standardize the application.

[figure not shown]
Sharp Debridement Therapy (control) group: Briefly, wounds may be rinsed with saline and blotted with sterile gauze prior to collecting baseline wound samples at Day 0. Wound measurements and wound photos will be taken on Day 0, Day 4, Day 7 (before and after sharp debridement) and on Day 8. Wound samples will be obtained on Day 0, Day 4, and Day 8. Sharp debridement will be performed by patient's wound clinician using standard technique on day 0 after baseline wound measures are obtained and again on day 7. Wound samples will be obtained by sterile swab(s) and 3-4mm curette scraping of wound bed using a sterile curette sweeping z track method across wound bed. Sterile filter paper or micropipette/capillary tube may also be used to collect wound fluid. Wound samples will be placed in appropriate receptacle for transport as described above. Wound gel dressing (with gauze as secondary cover) will be applied to wound after debridement and changed daily as a control dressing. The following depicts the anticipated sampling timeframe for each participant.

LDT group (X denotes sampling procedure)

- Day 0 - **X** pre-measures (**sample 1**); surveys; photos
Apply larvae bag 1
- Day 4 - Remove larvae bag 1

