X post-measure (**sample 2**); Pain survey; photos
Apply larvae bag 2
- Day 8 - **X** final measures (**sample 3**); surveys; photos

SD group

- Day 0 - **X** pre-measures (**sample 1**); surveys; photos
Sharp Debridement 1
- Day 4 - **X** post measures (**sample 2**); pain survey; Wound photos
- Day 7 - Sharp debridement 2 & photos
- Day 8 - **X** final measures (**sample 3**); surveys; photos

Data Collection & Data Management

Measurement of bacterial colonization. A microbiological assessment of the wound samples will be performed. Samples will be measured for both planktonic (single) bacteria and biofilm bacteria by standard clinical microbiology techniques with serial dilution and plating on complete agar medium

plates. Colony forming units (CFUs) will be measured after approximately 24 hours of culture under standard laboratory conditions. Levels of planktonic bacteria and biofilm bacteria will be compared within each sample and chronologically within each patient. Photos will be reviewed by blinded wound clinicians and rated on amount of necrotic tissue present visually in wound bed at each sampling time (reported on scale 0 – 10 based on 0%, 1 = 10% or less, etc.). Data collected from human subject's electronic health record will include characteristics such as wound etiology, wound location/duration, wound treatments, wound photos, wound progress notes, age, gender, comorbid conditions, pertinent laboratory values and medical history. This data will be conducted only by trained research team members designated in the IRB approved study protocol over the duration of the study.

Only de-identified pertinent information per subject sample such as age of subject, visit number (Day 0, 4, 8), location of wound, duration of wound, co-morbid conditions, medications and current wound treatments will be shared with the investigational laboratories or their personnel. Only the PI, site PI, Co-Investigators, and study coordinator(s) will have access to the subject PHI and study folders. UF lab has agreed to destroy any remaining samples at the conclusion of the current study.

Measurement of MMPs. Using techniques such as ELISA or fluorescence resonance energy transfer (FRET) assay methodology, the levels of active MMPs (or measures of MMP activity) will be calculated and expressed as pg/ml of wound fluid and pg/mg protein.

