Measurement of IL6. Using techniques such as ELISA and fluorescence resonance energy transfer (FRET) assay methodology, the levels of active IL6 will be calculated and reported.

Methods for Data Collection & Data Management

Variable	Significance	Sampling time	Source	Specific Aim
Age	Demographic	Baseline	EHR	n/a
ABI	Exclusion criterion	Baseline - enrollment	ABI done after ICF	n/a
% nonviable wound tissue	Appearance of wound bed	Baseline Day 0 and Day 8	Provider assessment	Aim 1
Quantitative Cultures (planktonic and biofilm)	Microbial identification	Day 0 (pre-test), + Day 4 and Day 8	Wound samples	Aim 1
Wound Size in cm ² (volume: L x W x D)	Descriptive	Baseline Day 0 and Day 8	Wound measurements	Aim 2
Interleukin 6	Marker of inflammation	Day 0 (pre-test), + Day 4 and Day 8	Wound sample (fluid and/or tissue)	Aim 2
Matrix metalloproteinases (MMP-2 and 9 equivalent)	Elevated MMPs associated with non-healing wounds	Day 0 (pre-test), + Day 4 and Day 8	Wound sample (fluid and/or tissue)	Aim 2
Perceptions of therapy	Perceptions of debridement	Day 0 (pre-test) + Day 8	Patient, Caregiver & Clinician Surveys	Aim 3

Survey Methods

Subjects will be asked to complete a paper survey at Day 0, Day 4 and Day 8 of the study, querying the patient's perceptions of: wound pain, satisfaction with most recent/current wound care method, ease of

care, effectiveness of most recent wound treatment, aesthetics of current wound treatment and toward sharp debridement and maggots for wound care.

Caregivers and wound clinical providers will be asked to complete a paper survey at Day 0 and Day 8 of the study (if wound clinician is caring for more than one study subject, they will be asked to complete a survey at day 0 of first subject, day 8 of first subject and 3 months later or at completion of the study for each type of debridement), querying them about their perceptions of what the patient's experience was regarding the most recent wound debridement methods as well as satisfaction with most recent/current wound care method, ease of care, effectiveness of most recent wound treatment, aesthetics of most current wound treatment and toward sharp debridement and maggots for wound care.

Data Analysis

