Data will be summarized with descriptive statistics. Data will be checked for implausible values, missingness, and distributional form. Data transformations will be made as necessary to achieve normality. To address Specific Aim 1 (comparing the clinical effectiveness of a self-contained larval debridement therapy with a bedside sharp debridement therapy), the numeric outcome measures of changes (post minus pre) in percent of non-viable tissue and bacterial biofilm will be analyzed using independent samples t-tests. To address Specific Aim 2 (comparing wound characteristics of larval debridement and bedside sharp debridement therapies) over time, longitudinal generalized mixed models (GLMMs) will be used with the dependent repeated measures being wound characteristics (e.g., inflammatory markers, wound size) and the independent variable of group assignment (larval versus sharp debridement). To address Specific Aim 3 (investigating patient, caregiver, and clinician perceptions of larval therapy dressings and bedside sharp debridement using self-reported assessments, independent samples t-tests will be used to analyze data measured at the interval level, Wilcoxon rank sum tests will be used to analyze data measured at the ordinal level, and chi-square tests (or Fisher exact tests in the case of data sparseness) will be used to analyze categorical data. All hypotheses testing will be two-sided using a level of significance of .05. Data will be analyzed as "intent to treat." SAS version 9.2 (Cary, N.C.) will be used for all analysis.

Data and Safety Monitoring Plan

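### Participants whose wounds heal too much to be sampled are removed after randomisation, so Day 8 outcomes that need no tissue sample are lost because of response

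*Combined protocol and SAP*

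**What the plan says.** The rule stands in section 6, at the end of the exclusion criteria for the veteran site, and is repeated for the second site: "if the participant has significant wound healing so that sampling is not possible after the initial sampling, they will be removed from the study". Participants are randomised after consent. Under Study procedures, baseline samples precede the first debridement on Day 0, and later samples follow on Days 4 and 8.

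For Aim 1, Data Analysis states that "the numeric outcome measures of changes (post minus pre) in percent of non-viable tissue and bacterial biofilm will be analyzed using independent samples t-tests". The day that counts as post is not given. The same section says that data are analysed as "intent to treat". It defines no analysis set, and it says missingness will be checked without saying how it will be handled.

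The variable table lists percent non-viable tissue and wound size at "Baseline Day 0 and Day 8". The source for non-viable tissue is "Provider assessment". The measurement section adds a second route: "Photos will be reviewed by blinded wound clinicians and rated on amount of necrotic tissue present visually in wound bed at each sampling time". Subject surveys are planned for Days 0, 4 and 8.

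**The concern.** Removal depends on how the wound responds after treatment has begun, so those removed are not a random subset of those randomised. If healing goes with the Aim 1 outcomes and one arm heals more, that arm loses more of its good responders and the comparison shifts. Recruiting more people restores numbers but does not remove this bias.

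Much of the loss is also avoidable. Being unable to curette a wound prevents measurement of biofilm and of markers taken from the sample. It does not prevent rating non-viable tissue (Aim 1), measuring the wound (Aim 2) or completing a survey (Aim 3).

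**Working it through.** **What is lost, by time of removal**

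- *First unsampleable at Day 4.* There is no biofilm value after baseline. The planned Day 8 non-viable tissue, wound size and survey values all fall after removal. The Aim 2 mixed model does not recover wound size, because the variable table gives it only at Day 0 and Day 8.
- *First unsampleable at Day 8.* Day 4 sample data exist, and Day 8 photos may exist. The Day 8 biofilm value is missing. Because post is undefined, it is unclear whether Day 4 would be used instead.

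**The plan's own figure**

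Sample Size Power Analysis gives 64 per group for an effect of 0.50, two-sided alpha .05 and at least 80% power. A two-sample t calculation (noncentral t) gives n = 63.77, rounded up to 64, with power 80.1%. The figure reproduces. With all 140 recruits (140/2 = 70 per arm), power is 83.6%.

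**How rare removal may be**

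Entry needs an ulcer over 8 weeks old and at least 1.5 cm across, and follow-up is 8 days. The point at which sampling becomes impossible is not defined. If it means a wound narrower than the 3-4 mm in the sampling description (an assumption), a 1.5 cm round wound must lose 1 − (0.4/1.5)² = 92.9% to 1 − (0.3/1.5)² = 96.0% of its area.

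**Size of the bias (illustration)**

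The inputs from the documents are 70 per arm, 0.50 SD and alpha .05. The rest is assumed. A latent healing score H has SD 1, and anyone with H > c is removed. H is shifted by 0.5 SD in the larval arm. H and the outcome have within-arm correlation ρ = 0.5. There are no other losses.

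For each arm, with a = c − mean(H) and L = φ(a)/Φ(a):

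- retained n = 70 × Φ(a)
- retained mean = μ − ρL
- retained variance = 1 − ρ²(aL + L²)

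Worked case, c = 2.5:

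- Larval arm: a = 2.0, L = 0.0552, removed 1 − Φ(2.0) = 2.3%.
- Sharp arm: a = 2.5, L = 0.0176, removed 1 − Φ(2.5) = 0.6%.
- Difference = 0.50 − 0.5 × (0.0552 − 0.0176) = 0.481 SD.
- Retained n is 68.4 and 69.6, and the variances are 0.972 and 0.989. The standard error is 0.1686, the noncentrality 0.481/0.1686 = 2.85, and power 80.9%.

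| c | Removed, larval v sharp | Difference (SD) | Power |
|---|---|---|---|
| none | 0 v 0 | 0.500 | 83.6% |
| 3.0 | 0.6% v 0.1% | 0.493 | 82.7% |
| 2.5 | 2.3% v 0.6% | 0.481 | 80.9% |
| 2.0 | 6.7% v 2.3% | 0.458 | 76.6% |

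**Checks on the model**

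- With ρ = 0 the difference stays at 0.500. Power is 83.0% (c = 2.5) and 81.8% (c = 2.0), so most of the fall in the last two rows comes from bias and the rest from lost numbers.
- With equal healing (2.3% removed in each arm, ρ = 0.5) the difference is 0.500.
- If the sharp arm heals more, the difference becomes 0.519 (c = 2.5) or 0.542 (c = 2.0), away from zero.
- With no true difference but unequal healing, a spurious 0.02-0.04 SD appears, and the test rejects in 5.1-5.7% of trials.

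**The case against.** The strongest reply is that this will hardly ever happen. Old ulcers of at least 1.5 cm seldom close within 8 days, the removal rates above are assumed, and the rarest scenario moves the estimate by less than 0.01 SD. That stands as a limit on size. It does not make the rule harmless, and if cases are rare, keeping them costs almost nothing.

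A second reply is that removal from the study is not the same as exclusion from analysis. This is right, and a reader who infers that the plan expressly drops these people from the analysis, or flatly contradicts "intent to treat", goes further than the text. The analysis section can be read as using available data by assigned arm. For someone removed at Day 4, however, no Day 8 value is planned. Photos and progress notes from the health record might fill the gap, but the plan does not say that this collection continues after removal.

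Two other inferences are not supported:

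- *What survives a Day 4 removal differs by arm for photos.* Study procedures say of the larval arm that "Wound measurements and wound photos will be taken at baseline and Day 8", and of the sharp arm that "Wound measurements and wound photos will be taken on Day 0, Day 4, Day 7" and again on Day 8. The study summary and the sampling timeline, however, list Day 4 photos for the larval arm too. Only Day 4 wound measurement differs, and the variable table does not use wound size at Day 4.
- *Healing removals push an 80%-powered trial to 77% or 73%.* Those figures apply the last two table rows to 64 per arm, so they assume that other losses have already used the whole allowance of 12 (140 − 128). Nothing says the 10% attrition excludes removal for healing. Part of the fall is lost numbers: with ρ = 0 and 64 per arm, power is 79.6% and 78.3%.

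**Conclusion.** The concern holds as a response-dependent removal after randomisation that loses Day 8 outcomes which could still be measured. It should be fixed, although the likely effect is small. In the illustration the bias is 0.01 to 0.04 SD on a true difference of 0.50 SD, with power of 83% to 77% against 84%.

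Those figures rest on assumed removal rates, an assumed 0.5 SD healing shift and an assumed correlation of 0.5. The bias is towards zero if the arm with the better outcome also heals more, and away from zero if the other arm heals more. There is none if healing is unrelated to the outcome or equal in both arms. A reader might infer that the rule must work against larval therapy, but the documents do not show which arm heals more within 8 days.

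**What to change.** In the exclusion criteria for both sites, replace removal with a statement that the tissue sample is not taken but the participant stays in follow-up to Day 8. Collect the Day 8 non-viable tissue rating, photos, wound size and surveys already planned, and analyse them in the assigned arm. State that post means Day 8 for Aim 1.

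For biofilm, add a code for not sampled because healed, and report its count by arm. Add one sensitivity analysis with a single pre-stated rule, for example the best rank on the change score in a rank sum test.

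Whether debridement continues in these participants is left to clinical management. Which rating of non-viable tissue is primary, and how other removals are handled, are separate questions.

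Cost: one sentence at each of two places, one definition, one case-report code and one sensitivity analysis, with no extra patients. The downside is a few more Day 8 assessments, and a sensitivity analysis that rests on an assumption about biofilm in healed wounds.

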The primary purpose of this study is to assess the efficacy of larval debridement therapy (LDT) with bagged, sterilized, live, medicinal blow fly (*Lucilia sericata*) larvae (or "BioBags") versus bedside sharp debridement in removing harmful bacteria, biofilm and necrotic tissue from chronic wounds to promote wound healing. Characteristics associated with chronic wound environments will be evaluated through analysis of samples of tissue taken from wound beds before and after both types of debridement. One hundred and forty patients \geq 21 years of age with an open, full thickness wound which is healing by secondary intention (of greater than 8 weeks duration and requires debridement) will be invited to participate. This recruitment number accounts for estimated 10% attrition rate, so final sample number is anticipated to be 128 subjects (64 in each arm). Samples of wound bed tissue and slough tissue (if present) will be collected on Days 0, 4 and 8 or prior to and after each larval debridement intervention or sharp debridement (control). Photos will be taken of the wound bed on Days 0, 4 and 8 or just prior to and after each debridement method. A randomized sampling procedure will place individuals into one of two groups: The intervention group will receive larval debridement therapy once every 4 days for 2 applications (with saline moistened gauze as cover dressing changed daily) and the control group will receive sharp debridement therapy every 7 days for 2 debridements (with wound gel dressing changed daily).

The wound and wound environment will be characterized by assessing wound Matrix Metalloproteinases (MMPs), inflammatory cytokines and the presence of total bacteria, planktonic (free floating) bacteria, and biofilm (sessile) bacteria. Clinicians will be asked to grade the amount of non-viable tissue apparent in the wound bed, appearance of any signs of infection and overall visual appearance of the wound at each visit. Wound size will also be assessed. Subjects will be asked to rate their wound related pain level at each visit before and after the debridement method is applied. Subjects, caregivers and clinicians will be asked to complete a short survey to self-report their perceptions of each method of debridement. Data will be analyzed using bivariate and multivariate methods.

4. **Background:**

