Data collection from human subject's electronic health record will include characteristics such as wound etiology, wound location and duration, wound treatments, wound photos, wound progress notes, age, gender, telephone number, comorbid conditions, pertinent laboratory values and medical history. This data will be collected only by trained research team members designated in the IRB approved study protocol over the duration of the study. Data collection will only occur in compliance with VA Information Security requirements. The Veterans selected for this study will be adults and may involve any age over 18, race/ethnicity, gender, and medical comorbid conditions. No special classes of subjects will be sought out.

Recruitment and informed consent: Wound care providers such as in podiatry and lower extremity or diabetic limb preservation program (DPM) and Wound Team Clinicians will be approached and the study will be described. They will be asked to notify study investigators of potential subjects who are likely to have chronic lower extremity or diabetic foot ulcers (> 8 weeks duration) of 1.5cm size or greater -and who may be interested in participating in the study. If Veteran says they are willing to participate, wound provider will notify investigator and one of research team will meet Veteran and wound provider in clinic. Study will be explained to Veteran and the Veteran will sign informed consent if they agree.

Non-Veteran site: adding North Florida Regional Medical Center as a second site to meet recruitment

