Setting, Sample: A target goal final sample size of forty adults (plus willing caregivers) from the North Florida Regional Medical Center will be recruited. Including the initial total target of 128 Caregivers and 6 Providers, and accounting for 12 caregivers lost to follow up or 10 subjects who fail screening, the total study recruitment population is still 296 for all recruitment sites. Wound providers and clinicians who care for lower extremity or diabetic foot ulcers will be provided with a "Provider Study Flyer" which gives a brief description of the study with inclusion/exclusion criteria listed (to remind the Provider to approach potentially eligible patients with Research Team Contact information). The clinicians will also be asked to give a Recruitment Brochure to potentially eligible patients (those with lower extremity or diabetic foot ulcers over 8 weeks duration). In addition, study flyers will be sent to select NFRMC wound and podiatry clinics. Providers will be asked to contact study team if any patient is willing to hear about the study. If the patient is willing to hear about the study, they may contact a study team member from the contact number on the recruitment brochure or the provider can let the patient know when the research team member is scheduled to be in the provider clinic office and the patient may talk directly to the research study team member for more information. If patients call a research team member, they will have their questions answered but will not be screened or consented over the phone. They will be scheduled to come into the provider office to discuss the study with a research team member and review informed consent. Members of the research study team will review the informed consent with

the patient and enroll the subject if they agree to participate. Wound clinicians will not be asked to consent subjects, or to provide a list of patients (PHI) to the research team. The subject's wound providers (clinicians) will be the ones to perform the sample collection and apply the LDT or bedside sharp debridement. The study sample also includes one available caregiver of the patient (non-professional) to answer the caregiver surveys if they are willing, and any willing wound care providers, who will be asked to answer the clinician survey regarding perceptions of debridement methods.

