Sample Size Power Analysis: Power analysis for the entire study is based on the patient sample and the primary study aim of comparing debridement methods on clinical effectiveness. The POWER procedure in SAS version 9.2 (Cary, N.C.) was used to conduct the power analysis. Assuming a Type I error rate of .05 and two-sided testing, a sample of 64 is needed in each group to detect a medium effect size of .50 with at least 80% power. This magnitude of effect is considered clinically significant.

Patient characteristics to be recorded: Age (in years), gender (Male/Female), presence of diabetes diagnosis (any "no" would be excluded from study), smoking behavior (Yes/No), presence or absence of pedal pulses (Yes/No) and Ankle Brachial Index (ABI), relevant laboratory values, culture reports and other pertinent medical history (co-morbid conditions). Additionally, telephone numbers will be obtained, with the participants consent, in order to call and remind the participant the day before their next upcoming visit.

Inclusion criteria: (1) Individuals over 21 years of age; (2) with chronic lower extremity or diabetic foot ulcers (wound duration over 8 weeks); (3) who at the clinician's judgment requires wound debridement (25% or more of wound bed covered with non-viable tissue); (4) wound size 1.5 cm (roughly the size of a quarter) or larger in diameter.

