Both groups will also receive standard care and therapies ordered by their health care providers for their chronic wound care (excluding systemic antibiotics and topical wound antimicrobials), and standard emergency contact numbers. The study duration for the participants is 8 days.

UF IRB and designated NFRMC and VA (as parent study site) approval(s) will be obtained as needed prior to beginning this research study. The total sample size (for all combined sites) is anticipated to be 140 total subjects (desired n=128 + 10% attrition).

Data collection from human subject's electronic health record will include characteristics such as wound etiology, wound location and duration, wound treatments, wound photos, wound progress notes, age, gender, telephone number, comorbid conditions, pertinent laboratory values and medical history. This data will be collected only by trained research team members designated in the IRB approved study protocol over the duration of the study. Data collection will only occur in compliance with UF IRB and study parent site (VA) Information Security requirements. The participants selected for this study will be adults and may involve any age over 21, race/ethnicity, gender, and medical comorbid conditions. No special classes of subjects will be sought out.

Recruitment and informed consent: Wound care providers such as in podiatry, and wound and hyperbaric clinics will be approached and the study will be described. They will be asked to notify study investigators of potential subjects who are likely to have chronic lower extremity or diabetic foot ulcers (> 8 weeks duration) of 1.5cm size or greater -and who may be interested in participating in the study. If patients say they are willing to participate, their wound provider will notify the study investigator(s) and one of the research team members will meet with the patient and wound provider in clinic. The study will be explained to the patient and if they agree to participate, the participants will sign informed consent.

Both Research Recruitment Sites:

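### A second, non-VA site was added, but the planned Aim 1 and Aim 2 analyses name no site term; adding one would gain modest precision and correct chance imbalance (low priority)

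*Combined protocol and SAP*

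**What the plan says.** Section 6, Research Plan, first describes a single Veteran site. It then introduces a Non-Veteran site: "adding North Florida Regional Medical Center as a second site to meet recruitment". The Setting, Sample paragraph for that site states: "A target goal final sample size of forty adults (plus willing caregivers) from the North Florida Regional Medical Center will be recruited". The overall size does not change: "The total sample size (for all combined sites) is anticipated to be 140 total subjects", of whom 128 are wanted for analysis. The sample-size paragraph is repeated for the second site with the same figures and is now said to cover the entire study: "a sample of 64 is needed in each group to detect a medium effect size of .50 with at least 80% power".

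There is one Data Analysis section, and it serves both sites. For Aim 1, changes (post minus pre) "in percent of non-viable tissue and bacterial biofilm will be analyzed using independent samples t-tests". For Aim 2, a longitudinal mixed model is fitted to the repeated wound characteristics with "the independent variable of group assignment (larval versus sharp debridement") as the only independent variable named. Neither aim mentions site as a covariate, a fixed or random effect, a stratum or a sensitivity analysis. The summary's reference to bivariate and multivariate methods names no covariate. Randomisation is described only as placing participants into one of two groups, with no statement on whether this is done by site.

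**The concern.** Several things that could influence the change in non-viable tissue or biofilm counts differ between the sites:

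- One site enrols Veterans and the other general patients.
- Background wound care is whatever each participant's own providers order.
- Each participant's own wound clinicians apply the treatment and take the samples. Sharp debridement and curette sampling both depend on the operator, and both feed the Aim 1 outcomes.

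If mean change differs by site, an unadjusted t-test leaves that variation in its error term. If the arms also contain different numbers of second-site participants by chance, part of the site difference passes into the treatment contrast with nothing in the analysis to remove it. The stated power is only just above 80%, so there is little room for avoidable variance. If site is not prespecified and the sites prove imbalanced, whether to adjust would have to be decided after the data are seen.

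**Working it through.** **Inputs from the documents.** Two-sided 5% level ("Assuming a Type I error rate of .05 and two-sided testing"); effect size 0.50; 64 per arm ("final sample number is anticipated to be 128 subjects (64 in each arm")); 40 participants at the second site. Counting the 40 within the 128 is an inference from the unchanged total; the share is then 40/128 = 0.3125.

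**Not in the documents.** No difference between sites in mean change is given. Every site effect below is an assumption, shown as a range.

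**1. The plan's own figure.** For a two-sample t-test the noncentrality is 0.50 × √(n/2). At n = 64 this is 0.50 × √32 = 2.83 on 126 degrees of freedom, and exact power is 80.1%. At n = 63 it is 79.5%. The stated 64 per arm is reproduced.

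**2. Chance imbalance.** Assume allocation is not balanced within site and the arms are 64 and 64. The number X of second-site participants in one arm is then hypergeometric (40 of 128, 64 drawn), with mean 20 and SD √[64 × 64 × 40 × 88 / (128² × 127)] = 2.63.

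| Difference between arms | Split | Probability |
|---|---|---|
| 8 or more | 24/16 or worse | 18.2% |
| 10 or more | 25/15 or worse | 8.5% |

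**3. Effect on the contrast.** Shift = site difference × (difference between the arms in second-site share).
- For an assumed site difference of 0.5 SD and a 24/16 split: 0.5 × (24 − 16)/64 = 0.0625 SD.
- The standard error of the contrast is √(2/64) = 0.177 SD, so the shift is 0.0625/0.177 = 0.35 standard errors.
- Relative to the target effect it is 0.0625/0.50 = 12.5%. It can go in either direction.

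**4. Precision, with 0.50 read in units of the total SD.** If site explains a share R² of the variance, the effect in residual units is 0.50/√(1 − R²).
- R² = 5%: 0.50/√0.95 = 0.513, power 82.1%.
- R² = 10%: 0.50/√0.90 = 0.527, power 84.1%.
- The unadjusted test stays at 80.1%. The figures are the same to one decimal with 125 or 124 residual degrees of freedom.

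**5. Precision, with 0.50 read in units of the within-site SD.** The site variance 0.3125 × 0.6875 × (site difference)² is added to 1 in the unadjusted analysis. Power with site in the model is 80.1% throughout.

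| Assumed site difference (within-site SD) | Site share of variance | Power, planned t-test |
|---|---|---|
| 0.25 | 1.3% | 79.6% |
| 0.50 | 5.1% | 78.1% |
| 0.75 | 10.8% | 75.5% |
| 1.00 | 17.7% | 72.1% |

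**6. Validity.** In simulation (20,000 trials per setting, simple allocation, no treatment effect, site differences of 0 to 1 SD) the unadjusted t-test rejected in 4.8% to 5.0% of trials.

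**The case against.** The strongest reply is that the planned analysis is valid, matches the power calculation, and loses little. Most of this stands.

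- **Validity.** Randomisation makes chance site imbalance part of the variation that the t-test's standard error already covers. A reader might infer an inflated false-positive rate; the simulation shows none.
- **Change scores.** Aim 1 analyses change, so site differences in baseline level cancel. Only a site difference in the change itself matters.
- **Similarity of the sites.** Podiatry and wound clinics are at both sites, clinical eligibility is the same apart from Veteran status, and one procedures section applies to both. That section includes sampling training, a training video for larval application, and transport of samples to the VA laboratory. Photographs are rated by blinded clinicians. A reader might take site as an established prognostic factor; the documents do not show that it predicts either outcome.
- **Deliberate choice.** The sample-size text was reworded to cover the entire study, and Data Analysis follows a heading for both sites. A reader might infer that the analysis was simply overlooked when the site was added; a deliberate choice of a simple analysis fits the text equally well.
- **Aim 2.** A longitudinal model for repeated measures over time implies time and subject-level terms, and subject effects would absorb part of a site difference. It would be over-reading to say the model contains group alone.
- **Allocation.** The mechanism is not described, so stratification by site is unstated rather than shown to be absent.

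What remains is that site is not named in either analysis, that it could plausibly affect the change because operators and background care differ, and that naming it costs almost nothing.

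**Conclusion.** The point holds as a refinement of precision, at low priority. It does not repair an invalid test. About 31% of the analysed sample may come from a second site, and neither the Aim 1 tests nor the Aim 2 model names site. On the total-SD scale, adjustment adds about 2 points of power if site explains 5% of variance and 4 points if it explains 10%. On the within-site scale, the planned test falls 0.5 to 8.0 points below the adjusted model for site differences of 0.25 to 1.00 SD. Chance imbalance of 8 or more second-site participants is not rare (18.2%), but with a 0.5 SD site difference a 24/16 split moves the estimate by only about a third of a standard error.

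These sizes rest on three assumptions: the forty lie within the 128, allocation is not balanced by site, and the site effects are of the sizes shown. If the sites do not differ in mean change, adjustment gains nothing and loses almost nothing. No size is computed for Aim 2, because the documents give no variance components.

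**What to change.** For Aim 1, replace each t-test with a prespecified linear model for the change with terms for arm, site and the Day 0 value of the outcome, and report the adjusted arm difference with its 95% confidence interval. The Day 0 values are already collected; their further gain cannot be computed because no pre-post correlation is given. For Aim 2, add site as a fixed effect to the mixed model and write out the time and subject terms that the text implies.

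The cost is about two residual degrees of freedom in Aim 1 (126 to 124) and slightly longer analysis wording. No new data are needed, since the enrolling site is known for every participant.

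Secondary: state how allocation is generated and whether it is done by site. If it is not, separate lists for participants still to be enrolled would limit further imbalance. That is a change to trial conduct rather than to analysis wording, and the case for the site term does not depend on it.
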